4.4 Supportive Care Guidelines

Subjects should receive appropriate supportive care measures as deemed necessary by the treating investigator. Suggested supportive care measures for the management of adverse events with potential immunologic etiology are outlined below and in greater detail in the ECI guidance document. Where appropriate, these guidelines include the use of oral or intravenous treatment with corticosteroids as well as additional anti-inflammatory agents if symptoms do not improve with administration of corticosteroids. Note that several courses of steroid tapering may be necessary as symptoms may worsen when the steroid dose is decreased. For each disorder, attempts should be made to rule out other causes such as metastatic disease or bacterial or viral infection, which might require additional supportive care. The treatment guidelines are intended to be applied when the investigator determines the events to be related to Pembrolizumab.

Note: if after the evaluation the event is determined not to be related, the investigator is instructed to follow the ECI reporting guidance but does not need to follow the treatment guidance (as outlined in the ECI guidance document). Refer to Section 4.2.1 for dose modification. It may be necessary to perform conditional procedures such as bronchoscopy, endoscopy, or skin photography as part of evaluation of the event. Suggested conditional procedures, as appropriate, can be found in the ECI guidance document.

4.5 Duration of Therapy

Patients will continue with pembrolizumab until disease progression or unacceptable toxicity, or until completion of 35 treatments of pembrolizumab (approximately 2 years), as long as in the Investigator's opinion they are benefiting from treatment and they do not meet any other discontinuation criteria. Once patients have been discontinued from study treatment, other treatment options (including compassionate use) will be at the discretion of the investigator. Subjects will receive olaparib according to the FDA approved package insert until disease progression or unacceptable toxicity.

In patients with initial disease progression substantiated by radiographic imaging per RECIST 1.1, study treatment may continue until repeat imaging is conducted, at least 4 weeks and no later than 8 weeks later, under the following conditions:

- No worsening of ECOG Performance Status
- No clinically relevant increases in disease-related symptoms thought to be associated with disease progression
- No requirement for intensified management of disease-related symptoms exists, including increased analgesia, radiotherapy, or other palliative care.

Disease progression can also be confirmed histologically, cytologically, or surgically, or by physical examination or other clinical signs, per PI discretion.

4.6 Duration of Follow Up

Primary and secondary response objectives will be met with approximately 1 month end of study follow-up for subjects discontinuing therapy due to progression. Subjects who discontinue trial treatment for a reason other than disease progression will move into the Follow-Up Phase and should be assessed every 12 weeks (56 ± 7 days) by radiologic imaging to monitor disease status, per standard of care for up to two years of total study participation. Every effort should be made to collect information regarding disease status until the start of new anti-neoplastic therapy, disease progression, death, or at end of the study.

4.7 Removal of Patients from Protocol

Patients will be removed from the study when any of the criteria listed in Section 5.15 apply. Notify the Principal Investigator, and document the reason for study removal and the date the patient was removed in the Case Report Form. The patient should be followed-up per protocol.

4.8 Subject Evaluability and Replacement Guidelines

- Subjects who withdraw from the study treatment prior to starting study intervention will be replaced.
- Subjects who receive at least one dose of study treatment (pembrolizumab and olaparib) will be included in the safety analysis.
- Subjects who do not complete at least 6 weeks (2 cycles) of study treatment (pembrolizumab and olaparib) will not be evaluable for efficacy and will be replaced.

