2.4 Endpoints

Therapy administered until documented progression by RECIST 1.1 criteria or unacceptable toxicity.

This trial is a pilot study to assess the objective response rate with immunotherapy. There are no preliminary statistical assumptions. Stopping rules described in Section 9.

First response assessments at 9 weeks; time interval for trial assessment is typical for time interval for assessment of response to standard of care therapy. Investigational therapy will not preclude subsequent standard of care therapy or subsequent investigational therapy.

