If the toxicity does not resolve or the criteria for resuming treatment are not met, the participant must be discontinued from all study interventions.

If the toxicities do resolve and conditions are aligned with what is defined in Table 3, the combination of olaparib and pembrolizumab may be restarted at the discretion of the investigator. In these cases where the toxicity is attributed to the combination or to

olaparib alone, re-initiation of pembrolizumab as a monotherapy may be considered at the principal investigator's discretion.

Dosing Interruptions:

Dosing interruptions are permitted in the case of medical / surgical events or logistical reasons not related to study therapy (e.g., elective surgery, unrelated medical events, patient vacation, and/or holidays). Subjects should be placed back on study therapy within 3 weeks of the scheduled interruption, unless otherwise discussed with the Sponsor. The reason for interruption should be documented in the patient's study record.

Table 3: Dose Modification and Toxicity Management Guidelines for Immune-related AEs Associated with Pembrolizumab monotherapy and IO combinations

General instructions:

- 1. Severe and life-threatening irAEs should be treated with IV corticosteroids followed by oral steroids. Other immunosuppressive treatment should begin if the irAEs are not controlled by corticosteroids.
- 2. Study intervention must be permanently discontinued if the irAE does not resolve or the corticosteroid dose is not ≤10 mg/day within 12 weeks of the last study intervention treatment.
- 3. The corticosteroid taper should begin when the irAE is \leq Grade 1 and continue at least 4 weeks.
- 4. If study intervention has been withheld, study intervention may resume after the irAE decreased to ≤ Grade 1 after corticosteroid taper.

irAEs	Toxicity Grade (CTCAE v5.0)	Action With Pembrolizumab	Corticosteroid and/or Other Therapies	Monitoring and Follow-up
	Grade 2	Withhold	• Administer corticosteroids (initial dose of 1 to 2 mg/kg prednisone or equivalent)	Monitor participants for signs and symptoms of pneumonitis
Pneumonitis	Recurrent Grade 2, Grade 3 or 4	Permanently discontinue	 followed by taper Add prophylactic antibiotics for opportunistic infections 	Evaluate participants with suspected pneumonitis with radiographic imaging and initiate corticosteroid treatment

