5.12 Tumor Assessments

Tumor assessments will be conducted according to protocol timeline at 9 week intervals, with CT, MRI or other appropriate imaging, as well as physical exam and clinical measurements as appropriate while on study drug during Year 1. Tumor imaging will be obtained every 12 weeks after drug discontinuation, per standard of care, or during Year 2 of study treatment. RECIST version 1.1 will be used in this study for assessment of tumor response. While either CT or MRI may be utilized, as per RECIST 1.1, CT is the preferred imaging technique in this study.

Bone scans will be performed at screening for any subject with known bone metastases and/or new bone pain and musculoskeletal complaints. During the study, bone scans will be performed as needed for evaluation of worsening and/or new bone pain and musculoskeletal complaints or if the site believes they have attained a Complete Response. If a subject has no known metastatic disease in the bone or active symptoms, a bone scan at baseline is not needed. A bone scan can be obtained at follow up if there are new symptoms of bone pain.

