9.2 Sample Size and Early Stopping

Clinical benefit is defined as complete response, partial response, or stable disease (if stable disease, lasting for at least four months). A proportion of patients with clinical benefit less than 15% will be of no interest. The new treatment would be of interest if the proportion of patients with clinical benefit is at least 41%. Simon's two-stage design (Simon, 1989) will be used. The null hypothesis: p<= 0.15 is against the alternative hypothesis p>= 0.41. In the first stage, 10 patients will be accrued. If there are 2 or fewer subjects with clinical benefit among these 10 patients, the study will be terminated. The probability of early stopping under the null is 0.82, and under the alternative is 0.16. Otherwise, 10 additional patients will be accrued for a total of 20. The null hypothesis will be rejected if 6 or more responses are observed in 20 patients. This design yields a 1-sided type I error rate of 5% and power of 80%.

The early stopping rule is based on responses in the first 10 patients, rather than dose limiting toxicity, as the study drug is FDA-approved at the current dose used in this trial, has a known and predictable rate of toxicity at the present dose, has been used in prior cohorts of breast cancer patients at the current dose, and there is no biological basis on which to expect excessive or unusual toxicity in the study cohort.

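### Replacing every treated patient who stops before six weeks leaves no all-treated efficacy analysis, and biases clinical benefit and ORR upward if early stoppers do worse

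*Combined protocol and SAP*

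**What the plan says.** Section 4.8 has three rules. Subjects who withdraw before starting treatment are replaced. Subjects with at least one dose enter the safety analysis. Patients failing to "complete at least 6 weeks (2 cycles) of study treatment (pembrolizumab and olaparib) will not be evaluable for efficacy and will be replaced". Because the first rule already covers those who never start, the third acts on treated patients, and it gives no exception by reason for stopping.

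Section 2.4 places the first scheduled scan after this cut ("First response assessments at 9 weeks"), and Section 5.12 agrees ("Tumor assessments will be conducted according to protocol timeline at 9 week intervals").

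Section 9.2 defines the tested endpoint: "Clinical benefit is defined as complete response, partial response, or stable disease (if stable disease, lasting for at least four months". It sets a two-stage rule on that endpoint: "In the first stage, 10 patients will be accrued", the trial stops if 2 or fewer benefit, and otherwise the null of 15% is rejected at 6 or more of 20. Section 9.3 bases the interim look on the first 10 subjects. Neither section says whether the 10 and the 20 are treated or evaluable patients. No part of Section 9 names an all-treated efficacy set or says that early stoppers count as failures.

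**The concern.** A patient who dies, progresses clinically or on an unscheduled scan, or stops for toxicity before week 6 leaves the denominator and is replaced by someone who gets past week 6. Membership of the efficacy set is thus decided by a post-baseline outcome that is likely to be related to benefit. Benefit through stable disease requires four months, so many early stoppers could not qualify.

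The route is narrower than all early progression. Progression first seen on the week-9 scan falls after the cut and stays in the set. Section 4.5 also allows treatment beyond a first radiographic progression: "study treatment may continue until repeat imaging is conducted, at least 4 weeks and no later than 8 weeks later".

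The rule can also discard usable data. Under Section 4.6, "Subjects who discontinue trial treatment for a reason other than disease progression will move into the Follow-Up Phase" and continue to be imaged. Under Section 4.2.1, "re-initiation of pembrolizumab as a monotherapy may be considered at the principal investigator's discretion". A patient restarted in that way before week 6 would, read literally, not have completed six weeks of both drugs although still on treatment.

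At stake is a go/no-go decision that turns on 3 of 10 and 6 of 20, where one or two replaced patients can change the outcome, and an ORR that may not describe the patients who start the combination.

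**Working it through.** **Inputs from Section 9.2.** Null 0.15, alternative 0.41, 10 patients in stage 1 (stop at 2 or fewer), 20 in total (reject at 6 or more). Stated: one-sided type I error 5%, power 80%, early stopping 0.82 under the null and 0.16 under the alternative.

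**Reproducing the design.** With X ~ Bin(10, p) in stage 1 and Y ~ Bin(10, p) in stage 2:

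- P(stop early) = P(X ≤ 2)
- P(reject) = sum over x = 3 to 10 of P(X = x) × P(Y ≥ 6 − x)

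At p = 0.15, early stopping is 0.820 and type I error 0.0498. At p = 0.41, early stopping is 0.152 and power 0.806. These agree with the stated figures to within rounding or about a point. There is no slack in the type I error.

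**Effect of the rule.** Let d be the share of treated patients stopping before week 6, b their benefit rate, and q the completers' rate. The documents give neither d nor b; both are assumed.

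- All-treated rate: p = (1 − d)q + d·b
- Completers' rate: q = (p − d·b)/(1 − d)
- Bias: q − p = d(q − b), which is positive exactly when b < q

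For example, with p = 0.15, d = 10% and b = 5%, q = (0.15 − 0.005)/0.90 = 0.161.

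Type I error when the all-treated rate is 0.15 but the test is run on completers:

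| | d = 5% | 10% | 15% | 20% |
|---|---|---|---|---|
| q at b = 0 | 0.158 | 0.167 | 0.176 | 0.188 |
| Type I error, b = 0 | 0.061 | 0.076 | 0.095 | 0.119 |
| Type I error, b = 5% | 0.057 | 0.067 | 0.078 | 0.092 |
| Type I error, b = 10% | 0.054 | 0.058 | 0.063 | 0.069 |
| Type I error, b = 15% | 0.0498 | 0.0498 | 0.0498 | 0.0498 |
| Null early stopping, b = 0 | 0.80 | 0.78 | 0.75 | 0.72 |

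If early stoppers do better than completers, the error falls below nominal: 0.030 at d = 10%, b = 30%.

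**Effect on the estimates.** With b = 0, a true all-treated rate of 30% is estimated as 0.30/(1 − d) = 31.6, 33.3, 35.3 or 37.5%. In counts for ORR, a reported 6/20 = 30% would be 6/21 = 29%, 6/22 = 27% or 6/24 = 25% with 1, 2 or 4 replaced non-responders.

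**Patients treated (b = 0).** Under Section 4.8 the expected number is [10 + 10(1 − P(stop at q))]/(1 − d). If all treated patients count, it is 10 + 10(1 − P(stop at p)). For d = 5, 10, 15, 20%:

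- All-treated rate 0.15: 12.6, 13.6, 14.7, 16.1 under Section 4.8, against 11.8.
- Completers' rate 0.41: 19.5, 20.5, 21.7, 23.1 under Section 4.8, against 18.2, 17.8, 17.3, 16.9.

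**Power if 41% describes completers (b = 0).** The all-treated rate is 0.41(1 − d), and power on the all-treated set is 0.759, 0.705, 0.645 or 0.579.

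**The case against.** The strongest reply is that the inflation is conditional. It depends on d, on b, and on which population the 15% and 41% describe. If both were set for six-week completers, the error rate holds. That reading is possible: the Summary of Changes shows that Section 4.8 and the clarified definition in 9.2 both entered in Version 5. This point stands, but the plan does not say so, and the result would then not describe patients who start the combination.

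Early stopping may also be uncommon. Eligibility requires ECOG 0 or 1 and a life expectancy of at least 16 weeks, treatment may continue past a first radiographic progression, and the first scheduled scan comes after the cut. At d = 5% and b between 0 and 10%, type I error is only 0.054 to 0.061. One replaced non-responder moves ORR from 30% to 29%, against an exact 95% interval for 6/20 of about 12 to 54%. This is a fair argument for the lower part of the range.

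The trial calls itself a pilot without prior statistical assumptions. But Section 9.2 sets a formal test with stated error and power, and the rule should keep to them.

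Three smaller points also stand. The single-drug restart is a narrow case: where corticosteroids are given, Table 3 requires a taper of at least four weeks before treatment resumes, so a restart before week 6 needs very early onset. ORR has no hypothesis of its own, so for ORR only the estimate is clearly affected. The word accrued in 9.2 could mean everyone entered, but it does not override the explicit rule in 4.8.

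**Conclusion.** The concern holds. As written, the plan removes and replaces treated patients because of a post-baseline event, keeps them for safety only, and offers no all-treated efficacy analysis. The direction is upward if early stoppers do worse than completers, which is likely but cannot be shown from the documents.

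If the 15% null refers to all treated patients, type I error lies between 0.0498 (equal outcomes) and 0.119 (20% stopping early, none benefiting). Values near 0.054 to 0.061 are the more plausible if early stopping is around 5%. If the rates refer to completers, the error rate is correct and the problem is one of interpretation. Either way, the plan should say which population is tested.

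**What to change.** Replace the third bullet of Section 4.8 with text to this effect:

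> The efficacy population is all subjects who receive at least one dose of either study drug, in order of enrolment. Only subjects who never start treatment are replaced. Subjects who stop before six weeks are classified from all tumour assessments available before any new anti-neoplastic therapy, including follow-up imaging under 4.6. For ORR, a responder has a documented CR or PR; everyone else, including subjects with no post-baseline assessment, is a non-responder. For clinical benefit, the 9.2 definition applies, and progression after it has been met does not undo it. Subjects who progress or die before meeting it, whose stable disease is not documented to four months, or who have no post-baseline assessment have no clinical benefit.

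In 9.2 and 9.3:

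- State that stage 1 uses the first 10 and the final rule the first 20 subjects of this population, and which population 15% and 41% describe.
- Use one term for both decision rules. Section 9.2 states its hypotheses on clinical benefit but rejects on responses and explains early stopping in terms of responses.
- Keep the six-week completers as a labelled sensitivity analysis.

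Two related passages need attention. The safety bullet in 4.8 names both drugs, and olaparib may start up to 3 days after pembrolizumab, so its wording should match the new definition; otherwise a patient could be in the efficacy set but not the safety set. Section 4.6 gives follow-up imaging as 12 weeks but brackets 56 ± 7 days, while 12 weeks is 84 days. The two must be reconciled, because the interval affects whether stable disease can be documented to four months after early stopping.

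The cost is one paragraph in 4.8 and a few sentences in 9.2 and 9.3. No extra patients are needed. With b = 0 and d = 5, 10, 15, 20%, about 0.8, 1.8, 2.9 or 4.3 fewer are treated on average under the null, and 1.3, 2.8, 4.4 or 6.2 fewer if completers' benefit is 41%. The price is a somewhat lower reported rate. If 41% was meant for completers, power falls to about 0.76, 0.71, 0.65 or 0.58; the stated 80% must then be restated, and recovering it would need a redesign. The documents do not give accrual status. If the stage 1 decision has already been taken, let it stand, date the change before the final analysis, and report both sets.

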5.0 STUDY PROCEDURES

Assessments performed exclusively to determine eligibility for this study will be done only after obtaining informed consent. Assessments performed for clinical indications (not exclusively to determine study eligibility) may be used for baseline values even if the studies were done before informed consent was obtained.

All screening procedures must be performed within six weeks prior to C1D1 unless otherwise stated.

Note: It is estimated that up to 100-200 patients may be screened on this protocol to determine eligibility based on HDR status.

5.1 Informed Consent

Consent must be documented by the subject's dated signature or by the subject's legally acceptable representative's dated signature on a consent form along with the dated signature of the person conducting the consent discussion.

A copy of the signed and dated consent form should be given to the subject before participation in the trial.

The initial informed consent form, any subsequent revised written informed consent form and any written information provided to the subject must receive the IRB/ERC's approval/favorable opinion in advance of use. The subject or his/her legally acceptable representative should be informed in a timely manner if new information becomes available that may be relevant to the subject's willingness to continue participation in the trial. The communication of this information will be provided and documented via a revised consent form or addendum to the original consent form that captures the subject's dated signature or by the subject's legally acceptable representative's dated signature.

5.2 Tempus HRD

Tempus HRD will be used to determine HDR status, for patients who do not otherwise qualify for the study based on BRCA status; Tempus HRD testing will not be performed on patients who qualify for the study based on BRCA status.

Archival tumor tissue samples (FFPE blocks or slides), as well as a normal sample type [blood (preferred), FFPE adjacent normal tissue, or saliva] will be sent to Tempus for testing. Refer to the Lab Manual and Tempus Specimen Guidelines.

In addition, de-identified clinical data elements will be shared with Tempus, as specified in the master agreement.

5.3 Pregnancy Test

Female subjects of childbearing potential should have a negative urine or serum pregnancy prior to study registration and re-tested within 72 hours prior to receiving the first dose of pembrolizumab. If the urine test is positive or cannot be confirmed as negative, a serum pregnancy test will be required.

5.4 Medical History

A medical history will be obtained by the investigator or qualified designee. Medical history will include all active conditions, and any condition diagnosed within the prior 10 years that are considered to be clinically significant by the Investigator. Demographic information will be collected at screening and will include ethnicity, age, and gender.

5.5 Physical Exam

The investigator or qualified designee will perform a full or directed physical exam as clinically indicated. Clinically significant abnormal findings should be recorded as medical history. The time points for physical exam are outlined in Section 5.14. After the first dose of pembrolizumab, new clinically significant abnormal findings should be recorded as AEs.

5.6 Vital signs

The investigator or qualified designee will take vital signs at screening, prior to the administration of each dose of trial treatment and as specified in the Trial Flow Chart. Vital signs include temperature, pulse, respiratory rate, weight and blood pressure. Height will be measured at screening only.

5.7 ECOG Performance Status

The investigator or qualified designee will assess ECOG status at screening, prior to the administration of each dose of trial treatment and during the Follow-up as specified in the Trial Flow Chart.

5.8 Laboratory Safety Evaluations

Details regarding specific laboratory procedures/assessments to be performed in this trial are provided in the table below.

Laboratory tests for screening should be performed within 10 days prior to the first dose of pembrolizumab. After Cycle 1, pre-dose laboratory procedures can be conducted up to 72 hours prior to dosing. Results must be reviewed by the investigator or qualified designee and found to be acceptable prior to each dose of trial treatment.

Hematology	Chemistry	Other
Hemoglobin	Albumin	Triiodothyronine (T3)
Platelets	Alkaline phosphatase	Free thyroxine (FT4)
WBC (total and differential)	Alanine aminotransferase	Thyroid stimulating hormone

	(ALT)	(TSH)
Absolute Neutrophil Count	Aspartate aminotransferase (AST)	Coagulation: PT, INR, aPTT
Absolute Lymphocyte Count	Creatinine or calculated creatinine clearance (CrCl)	
	Calcium	
	Glucose	
	Potassium	
	Sodium	
	Total Bilirubin	
	Blood Urea Nitrogen	

